Text Message Intervention for Alcohol Use and Sexual Violence in College Students

NCT05065918

June 29, 2023

Study Protocol

A randomized control trial to assess the full trial protocol and to generate estimates of multi-target intervention efficacy compared to an alcohol use reduction TM intervention. This aim will also explore gender and SV exposure as potential moderators of the intervention's effects.

Scientific Premise: Data from Aim 2 student participants will be used to systematically review message content and decision trees by the mentorship team and SAG. Study procedures will also be reviewed and revised using data obtained from campus faculty/staff during Aim 2. The pilot randomized trial will examine the potential efficacy of the multi-target TM-delivered intervention among college students seeking care from campus health centers. We will also begin to explore two hypotheses, that the multi-target intervention will show: 1) greater decrease in alcohol use than the alcohol use reduction condition and 2) greater increase in the use of SV harm reduction behaviors than the alcohol use reduction control condition. Intermediate outcomes of SV harm reduction behavior knowledge and self-efficacy will also be assessed. Exploratory analysis will be conducted to examine potential moderation effects of gender and SV history on the intervention's effectiveness. To achieve this aim, we will recruit 200 students from campus health centers. Findings from this aim will inform an R01-scale RCT of the multi-target TM intervention. Following intervention completion, a sub-group of participants will be invited to participate in semi-structured interviews to elicit feedback on their experiences participating in the intervention.

Setting: This phase of the intervention will continue to build on existing relationships from [name] campus health center work (See stakeholder letter of support). Student recruitment, eligibility requirements, screening and consent procedures will be as described in Aim 2 (the addition of recruitment sites will be used, as needed, to achieve the proposed sample size). Eligible students will complete baseline measures and be randomized via computer to the intervention (multi-target SV/alcohol use messaging) or control (alcohol use reduction messaging alone) condition. To examine potential moderators of intervention effect, stratified randomization will be used to ensure an equal distribution of students by gender and SV history.

Intervention condition: The multi-target intervention will use a similar model to the alcohol use reduction intervention developed by [name].¹³⁻¹⁵ Students will be: 1) queried via TM prior to planned drinking days regarding both alcohol use and SV harm reduction goal setting; 2) provided with goal reminders during drinking period; and 3) assessed for goal attainment and given feedback following drinking episodes. Message library tailoring based on gender and prior SV victimization is anticipated, and will be developed and modified with feedback obtained during Aim 1 focus groups and from the SAG. Gender-based tailoring will likely include addressing risks/fears that are associated with or specific to different sex/gender categories (e.g. risk of pregnancy for women, fear of being accused of SV among men, gender-specific statistics). Development of gender neutral bystander intervention, help seeking, and harm reduction behavior language is anticipated. Prior SV victimization tailoring is anticipated to include messaging regarding coping with trauma and sharing of campus and community resources, while SV perpetration history tailoring will remain focused on universal

education regarding consent, and risk reduction techniques such as alcohol use reduction and use of social support mechanisms to monitor behavior while drinking (e.g. planning with friends how the group will get home after a night out).

Control condition: The control condition will be the TM-delivered alcohol use reduction intervention developed by [name].¹³⁻¹⁵ This intervention has been tested in young adults (age 18-25) recruited from Emergency Department and college settings, and will be used to provide an attention control group for efficacy testing. Prior to typical drinking occasions, individuals planning a drinking event are prompted to consider committing to a drinking limit goal, i.e.: “Would you be willing to set a goal to drink less than X drinks when drinking?”. Based on willingness to commit to the goal, a feedback message is provided. During typical drinking periods, individuals receive a goal reminder. The following day, the program provides goal success/failure feedback or drinking quantity feedback. For example, those occasions where an individual committed to a drinking limit goal triggers either messages to reinforce goal successes or reframe goal failures. When an individual did not commit to a drink limit goal, they are provided feedback based on alcohol quantity (e.g. abstinence feedback, high risk drinking feedback).

Sample, data collection, and measures: Inclusion criteria, data collection time periods and measures for the efficacy pilot will occur as detailed in the Aim 2 feasibility pilot, with the addition of a third time point three months following the end of the intervention (T3).

Analysis: Assessment of the full trial protocol will be conducted using descriptive statistics, including proportion of those recruited who are willing to be randomized, proportion adherent to the intervention and control treatments, and proportion who are retained three months post-intervention. These estimates will be crucial to design and success of a larger R01-scale study. In addition to descriptively assessing the full RCT protocol, we will conduct analyses of the specified exploratory outcomes, which serve as the basis for the full-scale study. Each exploratory outcome: 1) number of drinking days per month, 2) number of binge drinking days per month, 3) use of SV harm reduction strategies, 4) knowledge of sexual violence and alcohol risk, 5) self-efficacy to obtain sexual consent, and, will be tested for differences between the intervention and control conditions at T2 and T3 using generalized linear modeling. All models will be adjusted for age, SV history, and gender. Imbalances between groups on additional baseline characteristics (e.g., relationship status, residence, other substance use) will be assessed, and if differences are noted, variables will be included in multivariable models. Following intention-to-treat principles, analyses will be conducted on all who were randomized to a condition regardless of degree to which they interacted with the intervention. The estimates found in these analyses, including baseline prevalence estimates and confidence intervals, will be used as the basis for sample size considerations in a larger R01-scale study. Due to the small sample size of this pilot study, we do not expect to be powered at α of 0.05, and will thus consider interactions terms at $p < 0.2$ worth exploring in stratified analyses. To assess the impact of missing data, we will compare the primary models (maximum likelihood) to full information maximum likelihood models; differences in results between the two models will be described. Participation biases and attrition analyses will be completed to inform future study design. The

effect sizes calculated from these data will be used to estimate sample size needed for each outcome at of 0.2 and two-sided α of 0.05 for subsequent study.

Sample size considerations: Assessing 70 students per arm (total n=140) that have completed the program and follow up would provide sufficient data on the full RCT protocol across multiple campuses as well as estimates of intervention effects. Assuming a conservative retention rate of 70% for the three-month post-intervention follow up, we would need to enroll 200 participants at baseline. While we do not anticipate having sufficient power in this pilot to detect statistically and clinically significant results, preliminary sample size calculations for each outcome of interest is provided in the Statistical Design and Power attachment.

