Analysis: Assessment of the full trial protocol will be conducted using descriptive statistics, including proportion of those recruited who are willing to be randomized, proportion adherence to the intervention and control treatments, and proportion who are retained three months post-intervention. These estimates will be crucial to design and success of a larger R01-scale study. In addition to descriptively assessing the full RCT protocol, we will conduct analyses of the specified exploratory outcomes, which serve as the basis for the full-scale study. Each exploratory outcome: 1) number of drinking days per month, 2) number of binge drinking days per month, 3) use of SV harm reduction strategies, 4) knowledge of sexual violence and alcohol risk, 5) self-efficacy to obtain sexual consent, and, will be tested for differences between the intervention and control conditions at T2 and T3 using generalized linear modeling. All models will be adjusted for age, SV history, and gender. Imbalances between groups on additional baseline characteristics (e.g., relationship status, residence, other substance use) will be assessed, and if differences are noted, variables will be included in multivariable models. Following intention-to-treat principles, analyses will be conducted on all who were randomized to a condition regardless of degree to which they interacted with the intervention. The estimates found in these analyses, including baseline prevalence estimates, will be used as the basis for sample size considerations in a larger R01-scale study. To assess the impact of missing data, we will compare the primary models (maximum likelihood) to full information maximum likelihood models; differences in results between the two models will be described. Participation biases and attrition analyses will be completed to inform future study design. The effect sizes calculated from these data will be used to estimate sample size needed for each outcome at $\beta = 0.2$ and two-sided $\alpha = 0.05$ for subsequent study.

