Sample size considerations: Assessing 70 students per arm (total n=140) that have completed the program and follow up would provide sufficient data on the full RCT protocol across multiple campuses as well as estimates of intervention effects. Assuming a conservative retention rate of 70% for the three-month post-intervention follow up, we would need to enroll 200 participants at baseline. While we do not anticipate having sufficient power to detect statistically and clinically significant results, we have provided preliminary sample size calculations for our outcomes of interest. We estimated within-subject correlations to be between 0.2 and 0.6 between baseline and follow-up assessments.

Alcohol use (Number of drinking days, number of binge drinking days): Assuming a within-person correlation of 0.4 in alcohol use between baseline and follow up assessment, analyzing 70 students per arm (total n=140) would provide 80% power at $\alpha=0.05$ to detect a standardized difference of 0.395 between intervention and control. This translates to a 2-day greater reduction (SD=5.1 days) in number of drinking days in the past 30 days compared to a reduction seen with the control arm program. Given initials results of the control arm program, this would bring the total change needed to 3 fewer drinking days in the past 30 days from baseline

(150% greater efficacy compared to control program messaging). Assuming a 1-day greater decrease is possible with this intervention (2 days overall), 410 participants would need to be enrolled per arm (820 total), given 30% attrition.

SV Harm Reduction Strategy Use: Estimating a baseline prevalence of using at least one strategy at 25%, We believe a meaningful increase in any use is 30%. To achieve 80% power at an $\alpha=0.05$, and assuming a within-subject correlation of 0.4 between baseline and follow-up assessment, we would need 876 participants in each arm at follow-up; with 30% attrition, we would need to enroll over 2,500 total participants, at baseline. This sample sizes, however, are beyond the scope of the project. We believe enrolling 200 at baseline is feasible, providing 80% power at $\alpha=0.05$ to detect a 75% increase in any use of SV harm reduction strategies after accounting for attrition.

References

2. Strauss A. *Qualitative Analysis for Social Scientists*. New York: Cambridge University Press; 1987.

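### The analysis text names only a generalized linear model at T2 and T3, with no within-student correlation or combined contrast, while the SAP's 80% power reproduces only with a two-measurement variance factor of 0.70

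*Protocol*

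**What the plan says.** The Analysis sections of both documents use the same sentence: each outcome is tested for arm differences "at T2 and T3 using generalized linear modeling". The Protocol adds "All models will be adjusted for age, SV history, and gender". The baseline value of the outcome is not among the listed covariates. Neither text mentions a random effect, a working correlation, a visit term, an arm-by-visit term or a pooled T2/T3 estimate.

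On missing data, both documents say "we will compare the primary models (maximum likelihood) to full information maximum likelihood models", without describing the structure of either model. The SAP also commits to intention to treat: "analyses will be conducted on all who were randomized to a condition regardless of degree to which they interacted with the intervention".

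Under Sample size considerations, the SAP writes "We estimated within-subject correlations to be between 0.2 and 0.6", referring to baseline against follow-up. It then uses 0.4 to obtain 80% power for a standardized difference of 0.395 with 70 students per arm. Both documents say that the effect estimates will be used to size the later R01 trial.

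**The concern.** Each retained student contributes two post-randomisation measurements. A standard generalized linear model treats rows as independent. Fitted separately at each visit, it gives two single-visit estimates, and the T3 fit makes no use of students who have T2 but not T3 data. Fitted to stacked rows, it ignores that two rows belong to one student. The text does not say which is meant.

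Two things are at stake. First, if the power figures assume a gain from two correlated measurements and the analysis does not deliver it, the stated 80% does not describe the planned test. Second, the pilot's product is an effect estimate for R01 planning, and the plan yields two candidates per outcome without saying which will be carried forward.

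**Working it through.** **Inputs from the SAP, Sample size considerations:** 70 per arm; standardized difference 0.395; 2 days with SD 5.1; rho = 0.4 (range 0.2-0.6, baseline to follow-up); 70% retention at T3; 25% baseline use of SV harm reduction strategies. Alpha is 0.05, taken as two-sided.

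**Assumptions not in the documents:** T2-T3 correlation 0.2-0.6; T2 retention 70-85%; equal variances at T2 and T3.

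**1. Reproducing the SAP's figures.** Detectable d = (1.960 + 0.842) × √(2f/70), where f is a variance factor. Power at d = 0.395 is Φ(0.395/√(2f/70) − 1.96).

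| Factor at rho = 0.4 | f | Detectable d | Power at 0.395 | n per arm, 25% vs 30% |
|---|---|---|---|---|
| None (one visit, unadjusted) | 1.00 | 0.474 | 64.7% | 1251 |
| Baseline as covariate, 1−rho² | 0.84 | 0.434 | 72.2% | 1051 |
| Change score, 2(1−rho) | 1.20 | 0.519 | 56.9% | 1501 |
| 1−rho | 0.60 | 0.367 | 85.5% | 751 |
| Mean of two measures, (1+rho)/2 | 0.70 | 0.396 | 79.8% | 876 |
| **SAP** | | **0.395** | **80%** | **876** |

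Only the last factor matches. It also gives 70 per arm for 25% vs 43.75% (the 75% increase), as stated. For the 1-day effect it gives 286 per arm, and 286/0.70 = 409 enrolled (stated 410). That last figure does not discriminate by itself: with no factor and no attrition the answer is also 409, because the factor and the retention rate are both 0.70. The 0.395 and the 876 do discriminate.

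**2. In days.** The SE of a single-visit arm difference is 5.1 × √(2/70) = 0.862. Power for 2 days is Φ(2/0.862 − 1.96) = 64%.

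**3. Variance of the T2/T3 average.** With the same 70 per arm at both visits, the ratio to one visit is (1+rho)/2: 0.60, 0.70 and 0.80 at rho 0.2, 0.4 and 0.6, a cut of 40%, 30% and 20%. At rho = 0.8 the ratio is 0.90, a cut of 10%.

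With 85 per arm at T2 and 70 at T3, and dropout only after T2, let V2 = 1/85, V3 = (1−rho²)/70 + rho²/85 and C = rho/85. The average has variance (V2 + V3 + 2C)/4. Relative to T3 alone (1/70) this is 0.54, 0.61 and 0.69 at rho 0.2, 0.4 and 0.6. The largest cut is therefore 46%.

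**4. The T3 contrast itself.** With complete data, a saturated joint model returned the same T3 estimate and SE as the separate fit, so the gain is 0%. With missing T3 data the gain is rho²(1 − n3/n2). At 85% T2 retention that is rho² × (1 − 70/85) = 0.7%, 2.8% and 6.4% at rho 0.2, 0.4 and 0.6.

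**5. Dropout bias at T3.** This is an illustrative scenario: in one arm only, the log-odds of returning at T3 fall by 0.5 or 1.0 per SD of T2 drinking, with 70/85 of T2 attenders returning. Mean T2 drinking among returners is then 0.085 or 0.154 SD too low. The bias in a T3-only estimate is rho × 5.1 × that shift. The smallest is 0.2 × 5.1 × 0.085 = 0.09 day and the largest is 0.6 × 5.1 × 0.154 = 0.47 day. A likelihood model that includes T2 largely removes it, provided dropout is explained by what the model contains.

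**The case against.** **The text does not exclude a joint model.** A reader might infer that the two visits cannot be linked and will never be combined. The documents do not say that. They do not state that separate models are fitted, and the full-information maximum likelihood comparison could use T2 data from students lost by T3. This stands: the defect is missing specification. The comparison does not cure it, because its structure is undescribed and it is set against the primary models as a check on missing data.

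**The variance cut belongs to another estimand.** A reader might infer that a joint model makes the planned T2 and T3 comparisons 20-46% more precise. It does not. That range applies to the T2/T3 average set against T3 alone, with T2 retention of 70-85%. T3 falls three months after messaging ends, so persistence is a legitimate separate question, and its precision hardly changes. Set against T2 alone with 85 per arm, the cut is about 17-35%.

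**The correlation is borrowed.** The SAP's 0.2-0.6 is for baseline to follow-up. A higher T2-T3 correlation shrinks the gain.

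**The factor does not reveal intent.** The 0.70 shows that the calculation combined two correlated measurements. It does not show that they were T2 and T3; the SAP attaches the correlation to baseline and follow-up. Nor is averaging shown to be the best precision gain available. If baseline-to-follow-up correlation is 0.6, adjusting for the baseline outcome cuts variance by 0.6² = 36%, against 20% for averaging at equal numbers.

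**It is a pilot that disclaims adequate power.** That limits the consequence. It does not remove it, since the estimates feed R01 planning.

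**Conclusion.** The concern holds as a mismatch and an omission. The SAP's power figures carry a two-measurement factor of 0.70 that the analysis text does not deliver. Read as a single-visit model, the planned analysis has about 65% power at 0.395, or about 72% with the baseline outcome added at rho = 0.4, against the stated 80%.

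A joint T2/T3 model would supply a defined average with 20-40% less variance than one visit at equal numbers, and up to 46% less than T3 alone if T2 retention is 85%. Both figures rest on an assumed T2-T3 correlation of 0.2-0.6; at 0.8 with equal numbers the cut is 10%. For T3 itself the precision gain is 0% with complete data and about 1-6% at 85% T2 retention. The further benefit is protection against a bias of about 0.1-0.5 day under the assumed one-arm dropout pattern, for which the documents give no evidence either way. The variance formulas suit continuous outcomes and are approximate for counts and binary use.

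The change is worth making, but the visit-specific estimates are not invalid without it.

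**What to change.** In both Analysis sections, specify for each outcome one likelihood-based repeated-measures model (linear or generalized linear mixed model) fitted to T2 and T3 together, with arm, visit, arm-by-visit and the planned covariates. A likelihood method is preferable to ordinary GEE, which does not remove bias when T3 dropout depends on T2 values.

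Report the T2, T3 and T2/T3-average contrasts. State in advance which one feeds the R01 calculation. Do not let the size of the arm-by-visit term decide: at this sample size a fading effect would often go undetected and be averaged away. Say how the full-information maximum likelihood comparison relates to this model.

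Then restate the power paragraph for the named contrast, giving the variance factor, which two measurements it combines, and the correlation assumed between them.

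The cost is revised wording and a standard routine, with no new data. The one downside is that the average is a different estimand and is harder to interpret if the effect fades, which is why the visit-specific contrasts stay in the report.

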TEXT MESSAGE INTERVENTION FOR ALCOHOL USE AND SEXUAL VIOLENCE IN COLLEGE STUDENTS

NCT05065918

JUNE 29, 2023

STATISTICAL DESIGN AND POWER

Aim 3: Conduct a pilot randomized trial to assess the full trial protocol and to generate estimates of multi-target intervention efficacy compared to an alcohol use reduction TM intervention. This aim will also explore gender and SV exposure as potential moderators of the intervention's effects.

Exploratory Hypotheses: The multi-target intervention will result in: a) greater decrease in alcohol use, and b) greater increase in the use of SV harm reduction behaviors, when compared to the alcohol use reduction condition

Primary Outcomes:

- 1) number of drinking days per month,
- 2) number of binge drinking days per month,
- 3) use of SV harm reduction strategies,

Secondary (Intermediate) Outcomes:

- 4) knowledge of SV harm reduction behaviors,
- 5) self-efficacy to use SV harm reduction behaviors

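### The p<0.2 rule decides which moderators get stratified results, so those results are selected for looking large, and the SAP contains no moderator analysis

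*Protocol*

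**What the plan says.** Moderation is part of the trial's aim in both documents. The Protocol's opening statement says "This aim will also explore gender and SV exposure as potential moderators", and the SAP under Aim 3 also plans to "explore gender and SV exposure as potential moderators". The Protocol's Scientific Premise sets the status: "Exploratory analysis will be conducted to examine potential moderation effects of gender and SV history". Its Setting paragraph gives the study of moderators as the reason for stratifying the randomisation by gender and SV history.

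The method is in one sentence of the Protocol's Analysis paragraph. Because the pilot is small, "we do not expect to be powered at α of 0.05", so the investigators will regard interaction terms with p<0.2 as "worth exploring in stratified analyses". The same paragraph lists five outcomes and says that each "will be tested for differences between the intervention and control conditions at T2 and T3 using generalized linear modeling".

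The SAP's Analysis paragraph follows the Protocol's closely but lacks the p<0.2 sentence and mentions no interaction term. Neither document states the number of interaction tests, the levels or expected split of the moderators, the precision of an interaction estimate, or what will be reported for terms above 0.2.

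**The concern.** A pilot meant to generate estimates is best served by estimates that have not been filtered on their own size. Here a p-value decides which moderators get subgroup results. With about 140 analysed, an interaction estimate reaches p<0.2 only if it is large, so the stratified results are a selected set and tend to overstate any real difference between subgroups. A reader cannot tell a flagged null term from a flagged real one, and a real moderator can easily go unflagged. The SAP gives no analysis for an aim that it names, so this one Protocol sentence is all there is to follow. At stake is what the next trial's team learns about gender and SV history, which the randomisation was stratified to study.

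**Working it through.** **Inputs.** From the Protocol's Analysis paragraph: threshold 0.2 (taken as two-sided), five outcomes, two visits (T2, T3). From the stated aim: two moderators. From the sample size sections: 70 per arm analysed, 140 in total. From the SAP's alcohol use paragraph: correlation 0.4, detectable difference 0.395 SD, SD 5.1 days. Assumed here: two-level moderators, normally distributed estimates, and 140 analysed at each visit.

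**1. The plan's own figure.** The detectable difference is (1.960 + 0.842) × √(2/70) × √f, where f is the variance factor for using the baseline value.
- f = 1 (no adjustment): 0.474
- f = 1 − 0.4² = 0.84 (baseline as covariate): 0.434
- f = 2(1 − 0.4) = 1.2 (change score): 0.519
- f = (1 + 0.4)/2 = 0.7: 0.396

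Only f = 0.7 reproduces the SAP's 0.395. The documents do not state the factor, so the results below cover f = 1, 0.84 and 0.7.

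**2. Flags when nothing is moderated.** 5 × 2 × 2 = 20 terms. Expected flags are 20 × 0.2 = 4, whatever the correlation between tests. The chance of at least one is:
- 20 independent tests: 1 − 0.8²⁰ = 0.988
- 20 tests, simulated with assumed correlations of 0.2-0.7 between outcomes and 0-0.6 between T2 and T3: 90-99%
- 12 tests (the three SAP primary outcomes): 1 − 0.8¹² = 0.931 if independent, about 91% with moderate correlation
- 10 tests (one visit): 1 − 0.8¹⁰ = 0.893 if independent, 82-87% at outcome correlations of 0.5-0.3

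**3. Interaction precision.** SE = 2√f / √(N·s·(1 − s)), where s is the subgroup share. With N = 140 and s = 0.5, √(140 × 0.25) = 5.916, so the SE is 0.338 (f = 1), 0.310 (f = 0.84) or 0.283 SD (f = 0.7). This is twice the SE of the main effect. A term is flagged only if its estimate exceeds 1.2816 × SE, that is 0.36-0.43 SD, or 1.9-2.2 drinking days at SD 5.1. The SAP's detectable main effect is 2 days.

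**4. Chance of flagging a real interaction of 0.395 SD.** This is Φ(0.395/SE − 1.2816) + Φ(−0.395/SE − 1.2816).

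| f | SE | flagged at p<0.2 | mean flagged estimate ÷ truth |
|---|---|---|---|
| 1 | 0.338 | 46% | 1.7 |
| 0.84 | 0.310 | 50% | 1.6 |
| 0.7 | 0.283 | 55% | 1.5 |

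The last column is the mean of the normal estimate given that it is flagged, divided by 0.395. With an 80/20 split the flag rate falls to 38-44%. If all 200 were analysed with an even split it would be 55-65%.

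**5. A null term that is flagged.** The mean of |z| given |z| > 1.2816 is 2φ(1.2816)/0.2 = 2 × 0.1755/0.2 = 1.755. Times the SE, this gives 0.50 (f = 0.7), 0.54 (f = 0.84) and 0.59 SD (f = 1). Times 5.1, it is 2.5, 2.8 and 3.0 drinking days.

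**6. Other effect sizes and a stricter threshold** (even split, f from 1 to 0.7). At p<0.2, a true interaction of 0.20 SD is missed 69-72% of the time and one of 0.79 SD only 7-15%. At p<0.05, the 0.395 SD interaction would be missed 71-78% of the time and overstated 1.85-2.15 times.

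**The case against.** The strongest reply is that the rule is a labelled exploratory screen in a pilot that openly disclaims power. A flag prompts a further look and claims nothing; four flags in 20 is what a 20% screen yields by design. The misses come from having 140 participants. On both misses and overstatement, 0.2 does better than 0.05 would. All of this stands, and it is why the point is minor and why a stricter threshold is not the remedy.

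Three stronger readings are tempting, and the documents do not support them.
- *False moderator signals are almost certain.* The 99% figure needs 20 independent tests and no true moderation. The count is inferred, and drinking days and binge days, or T2 and T3, are plausibly correlated.
- *Selective reporting is planned.* The Protocol says which terms merit stratified analysis. It does not say that other interaction estimates go unreported; reporting is simply unspecified.
- *Exaggerated subgroup effects will size or steer the R01.* The sizing sentence concerns effect sizes for each outcome. Only the general statement that the aim's findings will inform the R01 could cover moderators. The Protocol's Intervention condition section bases message tailoring on focus groups and the SAG.

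It is also fair to say that reporting everything adds no power, and that 20 interaction and 40 subgroup estimates could still be picked over informally. But the reader would then see the whole set with its uncertainty.

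**Conclusion.** The point holds as a low-cost improvement. Choosing stratified results by p<0.2 yields a set selected for size. If nothing is moderated, four flags are expected from 20 terms and at least one is very likely. A real 0.395 SD interaction is flagged about half the time and then overstated by roughly half to 70%. A flagged null term looks larger on average than the 2-day main effect on which the SAP's power statement rests. The low flag rate is a consequence of the sample size; the selection of what is shown in strata is a consequence of the rule.

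The figures assume two-level, evenly split moderators, continuous outcomes and 140 analysed at both visits. The 70% retention is stated for the three-month follow-up, so T2 may have more. The SAP sizes SV strategy use as a proportion, so the SD-scale results do not carry over to it directly. Uneven splits or more levels would make matters worse; larger interactions would make them better. The SAP's silence on an aim that it names needs no assumption.

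**What to change.** Replace the p<0.2 sentence with a reporting rule. For every outcome and visit, give the arm-by-gender and arm-by-SV-history interaction estimates and the subgroup-specific effects, each with a 95% CI and all taken from the interaction model, whatever the p-value. State the number of interaction terms, label the set exploratory, and say that no moderator claim and no R01 sizing will rest on estimates selected by p<0.2. Put the same text in the SAP's Analysis section so that the two documents agree.

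The cost is wording in both documents and one longer supplementary table. No extra data are needed. The downside is more exploratory estimates to present, many with wide intervals.
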